1.0 General Information		
*Enter the full title of your study:		
Prospective Randomized Evaluation of the Denali and Option Inferior Vena Cava Filters		
*Enter the study number or study alias		
Option and Denali * This field allows you to enter an abbreviated version of the Study Title to quickly identify this study.		

5.0 Initial Screening Questions - Updated 9/13 In the result of the new form check questions 5.4 5.6, 5.7 5.8 Ind 5.10 before saving and continuing to the next section 5.1 * Application type: © Full Committee © Expedited © Exempt 5.2 * Risk level (Help Text updated 9/13): © Minimal risk © Greater than minimal risk 5.3 * Subject contact:

5.4 * Funding (past or present):	
 Funded or will be funded (external sponsor, gift, program or specific internal or departmental funds) Unfunded (no specific funds earmarked for this project) Unfunded student project 	
5.5 * The Principal Investigator and/or one or more of the key study personnel has financial intererelated to this study:	sts
C Yes O No	
If Yes , the Conflict of Interest Advisory Committee (COIAC) office may contact you for additional information.	
5.6 * This is an investigator-initiated study:	
⊙ Yes C No	
5.7 * This study ONLY involves retrospective records review and/or identifiable biospecimen analysis	sis:
C Yes ⊙ No	
5.8 * This is a clinical trial:	
5.9 * This is a multicenter study:	
C Yes • No	
5.10 * This application involves the study of unapproved or approved drugs, devices, biologics or in diagnostics:	ı vitro
⊙ Yes ○ No	
5.11 * This application involves a Humanitarian Use Device:	
 No Yes, and it includes a research component Yes, and it involves clinical care ONLY 	
5.12 * This study involves human stem cells (including iPS cells and adult stem cells), gametes or embryos:	
No Yes, and requires CHR and GESCR review	

UCSF IRB: 14-13307 NCT02201277 O Yes, and requires GESCR review, but NOT CHR review	6 of 32
5.13 * This is a CIRB study (e.g. the NCI CIRB will be the IRB of record):	
C Yes ⊙ No	
5.14 * This application includes a request to rely on another IRB (other than NCI CIRB):	
C Yes ⓒ No	
Note: If this request is approved, the CHR will NOT review and approve this study. Another institution will be the IRB of record.	

7.0 Study Design

7.1 * Study design (Help Text updated 9/13):

This is a prospective, randomized trial comparing two FDA-approved inferior vena cava filters, the Denali retrievable IVC filter (Bard Peripheral Vascular Inc., Tempe, AZ) and the Option Elite (Argon Medical, Athens, Texas).

Patients scheduled for IVC filter placement at UCSF Department of Interventional Radiology (IR) will be asked by the IR physician at either UCSF Mt. Zion, Moffitt or the new Mission Bay hospital if they wish to participate in this prospective, randomized study. Recruitment will be conducted by the physicians performing the IR procedures only. No additional recruitment calls, emails, posters or web pages are necessary. All procedures and the randomization to one of the two experimental groups will be carefully explained before obtaining and having participant signed written consent.

Screening:

Screening will be conducted by the IR physician prior to the placement of the IVC filters. Since this is a standard of care study, patients who are recommended for IVC filter placement and are scheduled for the procedure are generally eligible.

The screening procedures are part of routine care before IVC filter placement and would be done even if patients did not join the study.

The study doctor will review the results of most recent routine care imaging scans (CT or MRI) of the abdomen and pelvis. This is done to confirm that the diameter of IVC is no wider than 2.8cm. Both filters are FDA-approved to be placed in an IVC with maximal diameter of 2.8cm.

The study doctor will also review ultrasound of the lower extremity, when available, to confirm that a blood clot was in fact present prior to performing the study. This ensures that patients who present for IVC filter placement are screened properly.

The following screening procedures should be done within 12 days before the IVC filter placement procedure as part of the standard of care.

- · A complete physical exam
- \cdot $\,$ The study doctor will ask about medical history and how well patient is able to do daily activities
- Routine care blood tests (about 2 tablespoons)
 - o This is to ensure that the INR and platelet count of the patient is within the safe limits to perform an invasive procedure.

After Enrollment:

If the screening procedures show that the patient is eligible and consents to take part in the study, IVC filter placement will occur after randomization.

After enrollment, the following procedures will be done during the study: Just as with screening, all of these procedures are part of regular IVC filter placement care.

Randomization:

Randomization will occur on the day of procedure or prior clinic visit with IR physician to either the Denali or Option IVC filter. All IR attending physicians on the protocol are familiar with placement of either filter type. Prior to opening study to accrual, 75 sealed security envelopes with the word Denali printed on a card inside and 75 sealed security envelopes with the word Option will be assembled by IR staff not involved in the research. The envelopes will be mixed up and placed in a bag. Computerized randomization programs and tables were considered but we feel the envelopes will work best as there may be limited time after patient is consented and procedure begins. This is especially true as some filters are placed emergently. Previous IR studies have used this randomization technique with great success.

Filter Placement:

Placement of an IVC filter involves the insertion of a plastic tube (catheter) into a vein in the neck. Some numbing medicine (Lidocaine) will be injected in the skin over the vein before the catheter is inserted. Intravenous medications will be given to induce moderate sedation (Fentanyl for analgesic and Versed for moderate sedation). Once the catheter has been placed into the vein, it will be advanced into the IVC. Once in correct position, x-ray contrast material (x-ray dye-Omnipaqe 350) will be injected through the catheter and x-ray pictures taken. A series of x-ray pictures will be obtained of the IVC. These pictures are taken as part of standard of care to determine the position of the renal veins with respect to the IVC. The

top of the filter must sit below the renal veins so it doesn't cause obstruction of the renal veins. In addition, pictures of the IVC are taken to serve as another tool in measuring the diameter of the IVC to make sure the diameter of the IVC is less than 2.8cm. This is particularly important in situations when a CT or MRI of the abdomen and pelvis is not available to have reviewed prior to the procedure. Once pictures are obtained and it is made certain that the IVC diameter is less than 2.8cm, the filter will be inserted through the catheter, and placed below the renal veins. During the placement procedure, positioning of the filter will be monitored with x-ray pictures. At the completion of the procedure the catheter will be removed and pressure will be applied to the insertion site until the bleeding has stopped. All of this is part of routine standard of care for placement of the filter. The doctor performing the procedure will be asked to complete a short questionnaire after IVC filter placement which will be attached to "Study Documents".

Follow-Up:

After the IVC filter placement procedure patient status will be followed by the interventional radiology doctors.

Per standard of care after IVC filter placement, patient will be monitored in the hospital for up to 1 hour after the procedure. If patient is in stable condition and sedation has resolved, they will return home the same day or returned to their hospital rooms.

A tentative appointment for follow up and filter retrieval will be ordered by IR physician at time of filter placement in APEX. This will ensure that scheduling and study staff will be aware that further patient and primary care follow-up is required.

Patient primary care physician and/or relevant medical staff will be telephoned one month after IVC filter placement to determine if patient is medically stable and suitable for IVC filter removal.

If IR and other doctors agree that IVC filter removal is recommended, patient will be scheduled to return for follow-up imaging and filter retrieval. If patient is not medically stable or still at high risk for blood clots, we will attempt to schedule a follow up one month later. Close contact with primary physician and patient will be maintained to ensure that filter is removed as soon as possible. APEX scheduling will be used to make sure follow up is performed at regular intervals.

At follow-up appointment these routine tests per standard of care before IVC filter removal will be performed:

- A physical exam
- · The study doctor will ask about medical history, how well patient is able to do daily activities, and if they are experiencing any possible symptoms related to the IVC filter placement such as abdominal or back pain.
- A rotation CT focused to the site of the filter will be performed as part of routine practice of filter removal. This is done to ensure the filter has not migrated or that the filter has not penetrated through the walls of the IVC such that filter retrieval would be unsafe.
- · IR physician will determine if patient status is stable and safe for IVC filter removal. If not, physician will discuss with primary care doctor if filter needs to remain permanently in patient or if later retrieval should be considered at subsequent follow up visits.
- · IVC filter retrieval will be performed under moderate sedation. This procedure is very similar in nature to the filter placement procedure. The IVC filter is removed via a similar process to the way in which it was placed. X-ray dye (contrast) will be injected around the filter to assure that the filter and the area beneath the filter are free of blood clots and that it is safe to proceed with removal. A catheter-based snare will be used to engage the hook at the end of the filter and the filter will then be enveloped by a removal sheath and removed from the body.

Imaging Analysis:

Single blind CT and x-ray imaging analysis will be conducted by a trained radiologist doctor using standard imaging tools and workstations (Agfa PACS V.6). The radiologist will be unaware which patient received which filter type to minimize any potential bias in searching for IVC filter complications.

The radiologist will be instructed to look for the following complications of the IVC filter per Society of Interventional Radiation (SIR) guidelines:

- Filter penetration as defined by more then 3mm penetration of IVC wall by one or more components of the IVC filter
 - o Also look for signs that other organs or spine were penetrated
- Filter tilt as defined by greater than 15 degrees tilt perpendicular to axis of IVC
- Filter migration as defined by more than 1 cm from initial filter location
- Filter thrombus as defined by clot formed in filter mesh
- Filter fracture as defined by breakage of one or more of filter components

0.1 Hunsthadia (Hala Tautumdatad 0./12).	

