10.0 Sample Size and Eligibility	
10.1 Number of subjects that will be enrolled at UCSF and affiliated institutions:	
150	
10.2 Total number of subjects that will be enrolled at all sites (Help Text updated 9/13):	
150	
10.3 Estimated number of people that you will need to consent and screen here (but not necessaril enroll) to get the needed subjects:	у
300	
10.4 Explain how and why the number of subjects was chosen (Help Text updated 9/13):	
The numbers are based on statistical power analysis and examination of our findings from previous IVC filter retrospective studies done by UCSF interventional radiology. The most recent study showed that one group of filters had 22% penetration and the other had 10% penetration. However, because the numbers in each group were too small, no significant difference in degree of penetration was found. For sample size, we determined that with \sim 75 patients per group and similar differences in incidence or penetration as our preliminary study (25) (22% & 10%) we will see a significant difference at the p = 0.05 level with power 80%. If the difference is a little wider (25% vs. 10%) we will see significance at 50 patients per group. This calculation is using a comparison of proportions test with a z-statistic.	
To make sure this will be feasible, we looked at the total number of IVC filters placed in the previous year at UCSF Mount Zion and UCSF Parnassus. In 2013, 169 IVC filters were placed in patients between the two hospitals. Since this is a standard of care study and no extra time committment will be required, we expect most patients will be consented and agree to be followed in the study. Over a two year proposed study timeline with on average 340 patients receiving IVC filters, we expect to consent about 300 patients in order to get the 100-150 needed to find significant findings. We expect half of the 300 consented patients to be lost to follow up and not return for follow up imaging and retrieval.	
10.5 * Eligible age range(s):	
 □ 0-6 years □ 7-12 years □ 13-17 years ☑ 18+ years 	

1. Patients scheduled for IVC filter placement at UCSF Moffitt, Mount Zion, or Mission Bay Interventional Radiology Service. 2. 18+ 1. Necessity of permanent IVC filter
Necessity of permanent IVC filter
1. Necessity of permanent IVC filter
2. Genetic or physical abnormalities of the inferior vena cava

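### The envelope may be opened before the on-table cavogram, even at an earlier clinic visit, so allocations can be wasted and the device is known while plans can still change

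*Combined protocol and SAP*

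**What the plan says.** On timing, section 7.1 (Randomization), repeated in 14.1, says: "Randomization will occur on the day of procedure or prior clinic visit with IR physician to either the Denali or Option IVC filter". On order, 7.1 (After Enrollment) says that, for an eligible and consenting patient, "IVC filter placement will occur after randomization".

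The cavogram belongs to the placement procedure. In 7.1 (Filter Placement), also in 14.1: "Once pictures are obtained and it is made certain that the IVC diameter is less than 2.8cm, the filter will be inserted through the catheter". The same paragraph calls this measurement "particularly important in situations when a CT or MRI of the abdomen and pelvis is not available to have reviewed prior to the procedure".

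There is an earlier check. Section 7.1 (Screening) has the study doctor review the most recent CT or MRI: "This is done to confirm that the diameter of IVC is no wider than 2.8cm". It adds: "Both filters are FDA-approved to be placed in an IVC with maximal diameter of 2.8cm".

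Other relevant provisions:
- Section 10.0 lists as an exclusion: "Genetic or physical abnormalities of the inferior vena cava". It also allows exclusion at the investigator's discretion.
- Section 7.1 provides 75 envelopes per device, 150 in all, and describes no spares.
- Under 15.2 and 15.3, the filter used off study is normally the physician's choice.
- Under 17.1 (Withdrawal), the patient or the attending physician can ask for the patient to leave the study.

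**The concern.** Allocation can be known before the last check on whether a filter will be placed. With clinic-visit randomisation it can be known well before, since the plan sets no limit on the interval. Two things follow.

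First, a patient whose envelope has been opened may receive no study filter. Such a patient can have no penetration outcome, and one of a fixed number of allocations is spent. Sections 7.1, 8.3, 10.0, 14.1 and 17.1 contain no replacement rule, no analysis population, and no rule for a patient who receives no filter or the other filter.

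Second, the physician who recruits also performs the procedure and cannot be blinded to the device. Once the device is known, the physician or patient has time to cancel, switch or withdraw, and off study the physician's preferred filter is available. If such decisions depend on the device drawn, the arms no longer compare like with like. The blinded image reader protects the assessment of scans, but cannot restore patients lost selectively before any scan exists.

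**Working it through.** **Sequence check (no arithmetic)**

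1. Screening: CT or MRI is reviewed against 2.8 cm where a scan exists (7.1, Screening).
2. Envelope opened: at a prior clinic visit, or at an unspecified time on the procedure day (7.1 and 14.1, Randomization).
3. Cavogram: taken on the table, within the placement procedure, which follows randomisation.
4. Filter inserted: only after step 3 confirms the diameter.

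For a patient with a prior scan, step 1 screens the diameter and step 3 confirms it. For a patient without one, step 3 is the first diameter check, and the plan allows it to come after step 2. Same-day randomisation can also precede step 3, so the clinic-visit option lengthens the gap but is not its only source.

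**Baseline power**

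Inputs from 8.3 and 10.4: 75 per group, 22% versus 10%, p = 0.05, z-test for two proportions. Sidedness is not stated; I take two-sided. With mean proportion p̄ = 0.16:

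Power = Φ{ [ |p₁ − p₂|√n − 1.96√(2p̄(1 − p̄)) ] / √(p₁(1 − p₁) + p₂(1 − p₂)) }

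At n = 75: [0.12 × 8.660 − 1.96 × 0.5185] / 0.5115 = 0.045, so power is 51.8%. The plan states 80%. That does not reproduce: one-sided power is 64.2%, and 80% two-sided needs 146 per group. This is a separate problem; here 51.8% serves only as the starting point.

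**Cost of lost allocations**

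Let s be the share randomised before the cavogram and f the proportion of those who then receive no study filter. Neither is in the documents; all values below are assumptions.

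Envelopes lost = 150 × s × f; n per arm = (150 − lost)/2.

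| s | f | Envelopes lost | n per arm | Two-sided power |
|---|---|---|---|---|
| 100% | 1% | 1.5 | 74.25 | 51.4% |
| 100% | 2% | 3 | 73.5 | 51.0% |
| 100% | 5% | 7.5 | 71.25 | 49.7% |
| 100% | 10% | 15 | 67.5 | 47.6% |
| 50% | 10% | 7.5 | 71.25 | 49.7% |
| 20% | 10% | 3 | 73.5 | 51.0% |
| 20% | 2% | 0.6 | 74.7 | 51.6% |
| 10% | 2% | 0.3 | 74.85 | 51.7% |

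At the upper bound the loss is 51.8 − 47.6 = 4.2 percentage points. Keeping 150 treated patients would then need 150/0.90 = 166.7, or 167 envelopes, against the 150 provided.

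The table assumes that every treated patient is assessed. Section 10.4 expects half of consented patients to be lost to follow-up. If half of those randomised were lost, n = 37.5 per arm gives 29.1%, and the same 10% loss of allocations gives 26.6%, a fall of 2.5 points.

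**Bias**

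The size limit is identical for the two devices, so exclusion on diameter should not depend on arm: it costs precision, not validity. The remaining route is discretionary, through cancellation, switching or withdrawal with the device known. The documents hold no figures from which to size it.

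**The case against.** The plan intends eligibility to be settled before allocation: screening imaging comes first, and the cavogram is described as a further tool for measuring diameter. Section 20.2 says that procedures are often scheduled the same day or are emergent, so clinic-visit randomisation may be uncommon. Attending physicians are said to know both filters, and nothing suggests that they would act differently by device. The expected loss to follow-up is far larger than any loss from this source.

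Most of this stands, and it limits the point. Four stronger readings are tempting but unsupported:

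- A reader might infer that diameter and anatomy are settled only on the table. The screening text shows otherwise for patients with prior imaging. The placement text gives the cavogram's purposes as renal vein position and diameter; its use as the check for the caval-abnormality exclusion is an inference.
- A reader might take 3 to 15 lost envelopes as the expected number. That range applies assumed rates of 2–10% to all 150 patients.
- A reader might infer that on-table diameter failures bias the comparison. The shared limit argues against that.
- A reader might think that removing the clinic visit is enough. It is not, because same-day randomisation can also precede the cavogram.

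What the objection does not remove is that the plan foresees patients without prior CT or MRI, leaves the envelope untied to the cavogram, and has no rule for an allocation used without a filter.

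**Conclusion.** The point holds as a cheap improvement with a modest benefit that cannot be quantified from the documents. Allocation can precede the check on which insertion depends. For patients without prior CT or MRI, eligibility can therefore fail after an envelope is used. The cost in precision is small: about 4 percentage points of power at an assumed upper bound of 10% of all 150, and less if fewer are randomised before the cavogram. The better reason to act is to avoid post-randomisation exclusions and to shorten the time in which a known device can influence who stays in the study. That bias is possible under the plan's rules but is not shown to occur. The plan is not contradictory or invalid on this point.

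**What to change.** In 7.1 and 14.1, remove the option to randomise at a prior clinic visit. State that consent is obtained before sedation, and that the next sealed envelope is opened in the procedure room only after the cavogram has confirmed eligibility and the operator has decided to place a filter. Add that everyone whose envelope is opened is reported by allocated arm, with the number and reasons for anyone who received no filter or the other device.

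This changes when allocation is revealed; the cavogram and placement steps stay as written. If followed, it brings the loss of allocations to on-table ineligibility to zero and leaves little time for discretionary changes once the device is known. The cost is one or two sentences in each section, having both devices at hand, and opening an envelope mid-procedure. The plan chose envelopes because time may be short, which suggests that this is workable, but it does not discuss allocation mid-procedure. The operators should confirm that it is practical.

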If yes, explain:	
14.4 Sharing of experimental research test results with subjects or their care providers:	
C Yes ⊙ No	
If yes, explain:	
14.5 * Specimen collection for future research and/or specimen repository/bank administration:	
C Yes O No	
14.6 Time commitment (per visit and in total):	
The total time commitment per subject would be the same as for any standard of care IVC filter patient. No additional study visits outside of IVC filter placement, retrieval and imaging are necessary. There may be brief follow up telephone calls by IR reception staff and research coordinators which will be minimal and only done for follow up and continuity of care.	
14.7 Locations:	
UCSF Moffitt hospital, Mission Bay or Mt. Zion hospital department of interventional radiology.	
14.8 Describe the resources in place to conduct this study in a way that assures protection of the ri and welfare of participants:	ghts
UCSF medical staff nurses, physicians and administrative staff involved in the standard of care procedures for patients already scheduled for IVC filter placement. 6 or greater interventional radiology physicians will also be on protocol and our trained extensively in IVC filter placement and monitoring. An independent radiologist will also be on key study staff to assist with the unbiased imaging analysis.	

In addition there is a dedicated clinical research coordinator that will facilitate patient care and contact, primary physician contact, data collection and IR staff coordination.

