15.0 Alternatives

15.1 Study drug or treatment is available off-study:

Yes

No

Not applicable

15.2 * Is there a standard of care (SOC) or usual care that would be offered to prospective subjects at UCSF (or the study site) if they did not participate:

If yes, describe the SOC or usual care that patients would receive if they choose not to participate:

The standard of care would be for the patient to receive and IVC filter without randomization or physician questionnaires. The type of filter is determined by physician preference.

15.3 Describe other alternatives to study participation that are available to prospective subjects:

To not be randomized to either the Denali or Option Elite IVC filter. Also the physician would not complete a questionnaire about filter placement. In this case, the filter used is usually determined by physician choice.

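### Allocation is drawn from envelopes mixed in one bag, with no fixed sequence, named drawer, draw log or reconciliation stated, so concealment and audit are not assured.

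*Combined protocol and SAP*

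**What the plan says.** The allocation procedure is one short paragraph under Randomization in section 7.1, repeated in section 14.1.

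- **Pool:** "75 sealed security envelopes with the word Denali printed on a card inside and 75 sealed security envelopes with the word Option".
- **Preparation:** these "will be assembled by IR staff not involved in the research".
- **Order:** "The envelopes will be mixed up and placed in a bag".
- **Timing:** "Randomization will occur on the day of procedure or prior clinic visit with IR physician to either the Denali or Option IVC filter".
- **Alternatives:** "Computerized randomization programs and tables were considered but we feel the envelopes will work best". The reason given is that time between consent and procedure may be short, especially for emergent placements.

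Three other statements bear on who is near the draw. Section 7.1: "Recruitment will be conducted by the physicians performing the IR procedures only". Section 21.2 gives the final eligibility decision to the interventional radiology (IR) attending physicians on the protocol. Section 15.2, on care outside the study: "The type of filter is determined by physician preference".

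The plan does not say who draws, whether envelopes carry numbers, whether draws are recorded or counted, or where the bag is kept. Section 14.7 lists three places of work: "UCSF Moffitt hospital, Mission Bay or Mt. Zion hospital department of interventional radiology".

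**The concern.** Concealment should make a valid allocation independent of the good intentions of the people nearest to it. That needs two things: the next assignment cannot be known or changed before the patient is committed, and a record shows afterwards that each assignment was used as it came.

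The sealed envelope meets the first need up to the moment it is opened. The second is not met. Drawing from a bag has no next envelope, so a second draw looks like a first. The operator has usually seen the patient's imaging, cannot be blind to the device, and would normally choose it.

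If patients at higher risk of penetration were steered towards one device, penetration (the primary complication), tilt and operator satisfaction could all be biased. None of the planned analyses in section 8.3 (comparison of proportions, correlation, log-rank, strut count) would reveal or correct this. The stated hypothesis is no difference, so a spurious or a masked difference would bear directly on the conclusion.

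**Working it through.** The plan gives no figure for allocation bias, so there is nothing to reproduce. The check has three parts.

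**1. What each safeguard covers**

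| Stage | Safeguard stated | Gap |
|---|---|---|
| Preparing envelopes | Sealed; assembled by IR staff outside the research | None evident |
| Order of use | Mixing in a bag | No fixed sequence; a number on an envelope would not serve as one |
| Drawing | None | Drawer not named |
| After opening | None | No log, no patient ID on the envelope, no reconciliation |
| Reading images | Radiologist unaware of device (7.1) | Protects outcome reading, not allocation |

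**2. How large a bias re-drawing could cause**

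The documents supply none of these inputs; all are assumptions.

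- Share of higher-risk patients, h: 30% to 50%.
- Penetration in higher-risk patients, a: 25% to 40%. In the rest, b: 7% to 10%.
- Proportion of unwanted draws in higher-risk patients that are re-drawn once, r: 25% to 50%.
- Every operator prefers the same device, and each draw is treated as 50:50.

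For a higher-risk patient, the chance of receiving the preferred device is p = 0.5 + 0.5 × r × 0.5. The higher-risk share is

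- preferred arm: h·p / [h·p + (1−h)·0.5]
- other arm: h·(1−p) / [h·(1−p) + (1−h)·0.5]

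The false difference is the gap between these shares times (a − b).

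- *Smallest corner* (h = 0.30, r = 0.25, a = 25%, b = 10%): p = 0.5625. Shares are 0.16875/0.51875 = 32.5% and 0.13125/0.48125 = 27.3%. The gap of 5.26 points × 0.15 gives **0.8 points**.
- *Largest corner* (h = 0.50, r = 0.50, a = 40%, b = 7%): p = 0.625. Shares are 0.3125/0.5625 = 55.6% and 0.1875/0.4375 = 42.9%. The gap of 12.70 points × 0.33 gives **4.2 points**.

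*Mixed preferences.* Section 14.8 gives six or more physicians. If six treat equal numbers and split 4:2, then in the largest corner p = (4 × 0.625 + 2 × 0.375)/6 = 0.542. Shares are 52.0% and 47.8%, and the difference falls to 1.4 points. With a 3:3 split p = 0.5 and it is zero.

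*Scale.* The planned difference is 22% − 10% = 12 points, so the upper end is about a third of it (4.2/12 = 0.35). The standard error of the difference at 75 per arm is √(0.22 × 0.78/75 + 0.10 × 0.90/75) = 5.9 points.

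**3. Would a count reveal it?**

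Under the same assumptions, the expected number of replaced draws per 150 patients is 150 × h × 0.5 × r: 5.6 in the smallest corner and 18.8 in the largest. If those envelopes were thrown away, the fixed pool of 150 would fall short by that number, and counting used and remaining envelopes against enrolled patients would show it. The plan requires no such count. A count would not show which patients were affected, and would miss an envelope resealed and returned.

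**The case against.** Several points on the other side stand.

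- **The drawer is not named.** A reader might infer from section 7.1 that the recruiting physicians draw. The documents do not say so, and section 14.8 describes a research coordinator who could. Likewise, that the envelopes are unnumbered is a reading of silence.
- **A re-draw is not undetectable.** A reader might conclude that it could never be found. The pool is fixed at 75 + 75 and the envelopes are sealed, so discards would show in a count. The defensible statement is that no count is required.
- **Real safeguards exist.** Uninvolved staff prepare the envelopes, all attending physicians are familiar with both filters, caval abnormalities are excluded, and the image reader is blinded. These limit the harm but do not connect an opened envelope to a patient.
- **The size is assumed.** No re-draw rate or favoured device appears in the documents, and even the upper figure is below one standard error.
- **Hospital imbalance is a lesser matter.** A reader might infer that device is confounded with hospital. With an assumed 25-patient hospital, the chance of a 16:9 or worse split from one bag is about 19%. But this is chance imbalance within one department (section 5.9 answers no to multicenter). Nothing in the documents says that penetration differs by hospital, and power barely changes: even a 90:60 split overall gives 47.8% to 52.6%, against 51.8% at 75:75.

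The sponsor's reason for envelopes, limited time, is fair. It supports an envelope at the bedside; it does not require an unordered bag.

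**Conclusion.** The concern holds as a weakness in concealment and audit, not as evidence of misconduct or of bias that has occurred. The plan states no fixed sequence, drawer, log or reconciliation, while the people who recruit, judge eligibility and place the device normally choose it themselves. That conclusion rests on the text alone.

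The size does not. The range of 0.8 to 4.2 percentage points depends on every assumed input and on a preference shared by all operators; with divided preferences it falls towards zero. Bias of that order would be hard to recognise in the results, which is a reason to prevent it by design. The change should be made because the protection is substantial and the cost small.

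**What to change.** Replace the bag in sections 7.1 and 14.1 with the following.

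1. The statistician generates a computer permuted-block list with varying block sizes.
2. IR staff outside the research fill opaque, sequentially numbered envelopes from that list.
3. The protocol names who opens the envelope. Before opening, that person writes the patient ID, date and time on it and in a log.
4. Envelopes are used strictly in order.
5. Used and remaining envelopes are periodically reconciled against enrolled patients; the monthly research meeting in section 17.1 would be a convenient occasion.

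The bedside envelope stays, so speed in emergent cases is kept. The cost is a short amendment and log sheets. A separate stack at each hospital would be practical but needs spare envelopes, because hospital sizes are not known in advance. Stratifying by hospital is optional and secondary; if it is done, the analysis should include hospital as a factor.
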